### **Safety assessment**

- Brief physical examination (e.g., height and weight) to be completed at screening and Week 6. To minimize the time spent in in-person visits given the risks presented by COVID-19, and allow families the option to complete as much as possible virtually, we will accept documentation from the participant's physician stating that the participant is in good health to participate in the trial to replace the physical exam at screening. The Week 6 physical examination will be conducted by the study team.
- Vital signs (e.g., temperature, pulse, respirations, blood pressure) to be completed at each in-person visit. We will not collect vital signs during virtual visits (e.g., screening, Week 2, Week 4), as we did not detect any differences in heart rate or blood pressure in response to CBD administration in the first cohort of participants. We have also not noted any reports in the literature on such effects. Vital signs will be collected at baseline/enrollment and Week 6 visits.
- Test of hepatic and hematological function to be completed at screening, Week 4 and Week 6. To reduce in-person visits, we will make decisions regarding the necessity of a Week 4 blood draw on an individual basis. If a subject's baseline blood draw suggests borderline clinical abnormalities (that did not meet the cutoff for exclusion), they will be required to complete a Week 4 blood draw at the outpatient lab out of an abundance of caution. Otherwise, blood draws will be limited to two – one at baseline and one at the final visit (Week 6) – rather than three.
- Plasma for quantifying CBD levels to be completed at Weeks 6.
- AE report: UKU Side Effects Rating Scale – Patient Version (97) to be completed by parent/guardian at the Week 2, Week 4, and Week 6 visits. The participant will also be involved in these interviews when appropriate. Each UKU Side Effects Rating Scale will be reviewed by the PI. Symptoms of possible hepatic injury (i.e., fatigue, nausea, vomiting, right upper quadrant pain or tenderness, fever or rash) will be specifically queried.
- Columbia-Suicide Severity Rating Scale (98) to be completed by the participant at screening, baseline/enrollment, Week 2, Week 4, and Week 6 visits and reviewed by the PI. The C-SSRS is a brief assessment of suicidal ideation and behavior validated for use across the lifespan; the C-SSRS maintains strong psychometric properties (98). Screening for suicidality is necessary given that Epidiolex is classified within the anti-epileptic drug (AED) class, and AEDs have been shown to increase the risk of suicidal thoughts or behavior.

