Endpoints:	
Primary Endpoint: Optimal dose of CBD in children and adolescents with ASD, defined as the dose at which the greatest proportion of participants respond in an individualized target symptom domain designated for each individual prior to beginning CBD treatment
 
Secondary Endpoints: Effect sizes of changes in symptoms from baseline of measures developed to assess ASD symptoms, symptoms often associated with ASD, and global functioning
 
Exploratory Endpoints: Effect sizes of changes in MRI signals (i.e., resting-state functional connectivity) from baseline to the final week of treatment

Study Population:	
Sample will include 30 male and female participants with ASD between the ages of 7 and 17 years old. Participants will have fluent speech and an estimated IQ greater than or equal to 80. Individuals of all races and ethnic origins are eligible for participation. Following the completion of the BOIN design, in Part 2 of the trial, we will recruit youth with clinical profiles that most closely resemble youth classified as responders in Part 1 of the trial.

Phase:	
This is a Phase 2 study.

Description of Sites/Facilities Enrolling Participants:	
The study will be conducted at the Child Study Center, Hassenfeld Children’s Hospital, NYU Langone Health.

Description of Study Intervention:	
Study intervention will be 98% pure CBD. The CBD will be Greenwich Biosciences, Inc.’s 100mg/mL oral solution, brand name Epidiolex (V). A Bayesian optimal interval (BOIN) design will be used, such that participants will be assigned to cohorts of size 3 receiving doses of 3, 6, or 9 mg/kg/day, depending on the treatment response of participants in prior cohorts.

Study Duration:	
The duration of the trial is approximately 100 weeks.

Participant Duration:	
Expected duration of subject participation is 8 to 10 weeks, with in-person visits scheduled every other week. Between in-person visits, participants will be contacted via secure email and/or phone to assess for the presence of AE.

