### 1.3 SCHEDULE OF ACTIVITIES (SOA)

Procedures	Screening	Study Visit 1 Enrollment/Baseline	Telephone Follow-Up 1	Study Visit 2	Telephone Follow-Up 2	Study Visit 3	Telephone Follow-Up 3	Study Visit 4 Final Study Visit	2-Week Post-Trial Telephone Follow-Up	4-Week Post-Trial Telephone Follow-Up	6-Week Post-Trial Follow-Up	3-Month Telephone Follow-Up(s) c
Informed consent and assent	X											
Demographics	X											
Medical, Psychiatric, and Treatment history	X											
Administer study intervention		X		X		X						
Concomitant medication review	X	X	X	X	X	X	X	X	X	X		X
Physical exam (including height and weight)	X*							X				
Vital signs	X*	X		X*		X*		X				
Test of hepatic and hematologic function a	X					X*		X				
Pregnancy test b	X											
Plasma for CBD levels								X				
Urine drug screen	X											
Adverse event review and evaluation			X	X	X	X	X	X	X	X		
UKU Side Effects Rating Scale				X		X		X				
Mock MRI scan	X											
MRI		X						X				
Aberrant Behavior Checklist (ABC)		X*						X			X	
Anxiety, Depression, and Mood Scale (ADAMS)		X*						X			X	
Anxiety Scale for Children – Autism Spectrum Disorder – Child version (ASC-ASD-C)		X*						X				
Anxiety Scale for Children – Autism Spectrum Disorder – Parent version (ASC-ASD-P)		X*						X			X	
Autism Diagnostic Observation Schedule – 2 nd Edition (ADOS-2)	X*											
Childhood Autism Rating Scale, 2nd Edition, High Functioning (CARS-2-HF)	X											
Autism Family Experience Questionnaire (AFEQ)		X*						X				
Autism Symptom Interview (ASI)	X											
Behavioral Inflexibility Scale (BIS)		X*						X			X	
Brief Observation of Social Communication-Change (BOSCC)		X						X				
Clinical Global Impression Scale – Improvement (CGI-I)								X				
Clinical Global Impression-Severity (CGI-S)	X	X						X				
Columbia-Suicide Severity Rating Scale (C-SSRS)	X	X		X		X		X				
Computerized Kiddie Schedule for Affective Disorders and Schizophrenia (KSADS-COMP)	X											
Home Situations Questionnaire – ASD (HSQ-ASD)		X*						X			X	
OSU Autism Clinical Global Impression: Severity Subscale	X	X						X				
OSU Autism Clinical Global Impression: Improvement Subscale								X				
Repetitive Behavior Scale – Revised (RBS-R)		X*						X			X	
Screen for Child Anxiety Related Disorders (SCARED), Parent Version		X*						X			X	
Sleep Disturbance Scale for Children (SDSC)		X*						X			X	
Social Responsiveness Scale, 2nd Edition (SRS-2)	X							X			X	

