#### 4.3 JUSTIFICATION FOR DOSE

Chronic CBD dosing up to 1500 mg/day has been reported to be tolerated well without AE (60-63); minor AE were reported after CBD use in children with epilepsy being treated with multiple other medications in doses up to 50 mg/kg/day (3, 27). Accordingly, we believe an upper limit of 9 mg/kg/day orally in our dose finding approach is reasonable and safe. Our proposed dosage range is substantially lower than most pediatric studies registered in ClinicalTrials.gov (accessed on 06 February 2018). Our dose range (3-9 mg/kg/day) is comparable to the only ongoing study specifically addressing behavioral symptoms in ASD (NCT02956226; dose range 1 mg/kg/day to 10 mg/kg/day). As mentioned, participants assigned to the highest dose (9 mg/kg/day) will be instructed to take half the dose (4.5 mg/kg/day, divided in two doses) per day for the first week of treatment before increasing to the full dose to minimize the chance for adverse events upon treatment initiation. This will go into effect when the next cohort of participants begin treatment with CBD; therefore, all participants who have already been enrolled will not be re-consented or informed of the changes.

The BOIN design, discussed in detail within the Dosing and Administration section of the protocol, was informed by the observation of dose-dependent inverted-U effects on social behavior in a mouse model of Dravet syndrome in which social effects were observed at lower doses than anti-seizure effects (2), the increased efficacy of CBD in reducing anxiety during a public speaking task at a moderate dose compared to a low and high dose (9), and correspondence with [name] regarding his clinical experiences in prescribing CBD to address associated symptoms of ASD. As noted, now that we've obtained data from 15 participants on the low and intermediate doses by implementing the BOIN design, we propose to test the remaining 9 mg/kg/day dose in up to 15 participants – within the originally approved accrual ceiling of 30.

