Parents/guardians of participants will be compensated for study participation, subject to IRB approval, at the rate of \$75/visit for the enrollment/baseline, week-4 and final visits, and \$40/visit for the other two visits. If they agree to participate in optional MRI scanning, they will also be compensated \$75 for each scan. A \$10 stipend will also be provided for visits that include blood draws and MRI scans (e.g., Screening Visit, Baseline Visit, Week-4 Visit if indicated, Week-6 Visit) to cover any additional travel expenses. This practice is standard for research projects which require substantial effort, and serves to distinguish research from standard clinical practice.

In addition to compensation and because the study will occur across approximately 10 weeks, participants will receive visit reminders to enhance participant retention. Further, multiple methods including telephone calls and secure email will be used for contacting participants throughout the study.

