Given our experience with the first 15 participants, we anticipate that at least 1/3 will be classified as responders. If none of the first 6 participants on 9 mg/kg/day are responders, then we would eliminate the dose and terminate the trial. A low, non-zero response rate, as shown below in Table 3, would also determine terminating the trial, as it would be tantamount to evidence that the optimal dose was 6 mg/kg/day, our initial starting dose.

**Table 3.** Dose elimination rules for cohorts 6 to 10

Cohort	1	2	3	4	5	6	7	8	9	10
Number of participants to be treated at the current dose	3	6	9	12	15	18	21	24	27	30
Dose administered (mg/kg/d)	6	6	3	3	6	9	9	9	9	9
Cumulative N of respondents	1	3	4	4	5	-	-	-	-	-
Terminate if # of responses <=						NA	5	6	7	

Thus, we propose to enroll at least six more participants on the dose of 9 mg/kg/day. If none of them respond, the cumulative number of respondents would remain 5, and we will discontinue the trial; if at least 1 responds within the first 6, we will enroll 3 additional participants. If the total number of responders remains 6, we will discontinue the trial. If the number of responders is 7 or more after 9 participants are enrolled, we will enroll an additional 3 participants for a total of 12 on this dose. If the number of responders does not increase beyond a total of 7, we will terminate due to likely futility.

Table 4 provides the operating characteristics of this design extension for a variety of true response rates.

**Table 4.** Operating characteristics of 9 mg/kg/day evaluation

	Dose 1	Dose 2	Dose 3	Dose 4	Dose 5
True response rate	0.1	0.2	0.3	0.4	0.5
Probability of early termination(%)	90.4	60.8	31.0	11.9	3.5

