#### 9.4.4 SAFETY ANALYSES

Safety endpoints will be analyzed as summary statistics during treatment and as change scores from baselines. Adverse events will be coded per the Medical Dictionary for Regulatory Activities (MedDRA). Each AE will be counted once only for a given participant. Adverse events will be presented in terms of severity, frequency, and relationship of AEs to study intervention by System Organ Class (SOC) and preferred term groupings. For each AE, start date, stop date, severity, relationship, expectedness, outcome, and duration will be reported. Adverse events leading to premature discontinuation from the study intervention and serious treatment-emergent AEs will be presented either in a table. The information included here should be consistent with the information contained within **Section 8.2, Safety and Other Assessments**.

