##### 10.1.1.2 CONSENT PROCEDURES AND DOCUMENTATION

Informed consent is a process that is initiated prior to the individual's agreeing to participate in the study and continues throughout the individual's study participation. Consent forms will be IRB-approved and the participant's parent/guardian will be asked to read and review the document. The research staff will explain the research study to the participant's parent/guardian and answer any questions that may arise. A verbal explanation will be provided in terms suited to the participant's parent/guardian comprehension of the purposes, procedures, and potential risks of the study and of their rights as research participants. Participants and their parent/guardian will have the opportunity to carefully review the written consent form and ask questions prior to signing. The participants and their parent/guardian should have the opportunity to discuss the study with their family or surrogates or think about it prior to agreeing to participate. The participant's parent/guardian will sign the informed consent document prior to any procedures being done specifically for the study. Participants and their parent/guardian must be informed that participation is voluntary and that they may withdraw from the study at any time, without prejudice. A copy of the informed consent document will be given to the participant's parent/guardian for their records. The informed consent process will be conducted and documented in the source document (including the date), and the form signed, before the participant undergoes any study-specific procedures. The rights and welfare of the participants will be protected by emphasizing to them that the quality of their medical care will not be adversely affected if they decline to participate in this study.

Importantly, while the COVID-19 pandemic still presents a risk to participants and staff, we will reduce the number of required in-person visits and instead conducting those visits virtually over WebEx. All procedures in the screening visit, with the exception of the blood draw, will be conducted virtually and will continue to be conducted virtually based on individual family preferences. Therefore, our written consent/assent processes will be conducted via WebEx, albeit in the same way it would be done in person. The parent/guardian will be provided the written consent form prior to the screening visit and

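### Section 9.4.4 names no growth reference, so a plain change in kilograms from screening to Week 6 includes normal growth and can slightly understate slowed weight gain

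*Combined protocol and SAP*

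**What the plan says.** Section 8.2, under Safety assessment, provides for "Brief physical examination (e.g., height and weight) to be completed at screening and Week 6". The Schedule of Activities (Section 1.3) has a matching row, "Physical exam (including height and weight"), marked at screening and at Study Visit 4. The vital signs listed in Section 8.2 do not include weight, so the scheduled starting weight is the screening one.

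Section 9.4.4 gives one general rule, "Safety endpoints will be analyzed as summary statistics during treatment and as change scores from baselines", followed by adverse event tabulations, and asks for consistency with Section 8.2. No z-score, percentile or other growth standard appears in the document.

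The study is single-group (Section 4.1) and enrols ages 7 to 17.9 (Section 5.1). Section 2.3.1 reports loss of appetite in 28% on CBD against 5% on placebo in epilepsy trials.

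On timing, treatment lasts 6 weeks. The synopsis states "Expected duration of subject participation is 8 to 10 weeks, with in-person visits scheduled every other week", and Section 5.4 says "the study will occur across approximately 10 weeks". Section 8.2 also provides for a gap of more than 8 weeks after screening.

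A physician's note may replace the screening examination (Section 8.2). Section 10.1.1.2 adds that "All procedures in the screening visit, with the exception of the blood draw, will be conducted virtually" and makes the continuation of this a matter of family preference.

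**The concern.** A child who is still growing and whose weight stays flat has fallen behind expectation, yet a change in kilograms records no change. A child whose gain is halved still shows a rise. Without a control arm, nothing in the design subtracts the growth that would have happened anyway. The time from screening to first dose also differs between children, so the growth included differs too.

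At stake is the reading of a safety summary. Part 2 gives the previously untested 9 mg/kg/day dose, partly to confirm the safety profile, and the trial is meant to inform a later RCT. A mean change near zero could be taken as more reassuring than it is.

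**Working it through.** The plan gives no figure for weight, so there is none to reproduce. The size has to be illustrated with assumed ranges.

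**Inputs from the documents**
- 6 weeks of treatment (synopsis).
- 8 to 10 weeks of participation (synopsis), read here as screening to Week 6. That reading is an assumption.
- 14 weeks if an 8-week screening gap precedes treatment (8 + 6). This is a contingency.
- Group sizes: 6 at 3 mg/kg/day and 9 at 6 mg/kg/day (Section 4.2). At 9 mg/kg/day, "we propose to enroll at least six more participants on the dose of 9 mg/kg/day", with possible totals of 6, 9, 12 or at most 15. Up to 30 pooled.

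**Assumed inputs**
- Normal gain of 2 to 7 kg a year while growing, 0 once growth is complete.
- SD of individual change of 0.75 to 1.5 kg.
- Reference SD of weight of 6 to 12 kg.

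**Step 1: direction.** Raw change = expected growth − shortfall. The raw change therefore understates the shortfall by exactly the expected growth.

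**Step 2: offset.** Expected gain = yearly rate × weeks / 52.

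| Rate (kg/year) | 6 weeks | 8 weeks | 10 weeks | 14 weeks |
|---|---|---|---|---|
| 0 | 0 | 0 | 0 | 0 |
| 2 | 0.231 | 0.308 | 0.385 | 0.538 |
| 7 | 0.808 | 1.077 | 1.346 | 1.885 |

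The range is 0.2 to 0.8 kg over 6 weeks and 0.3 to 1.3 kg over 8 to 10 weeks. If gain is halved over 6 weeks, the raw change is still positive: 0.231 / 2 = 0.12 kg to 0.808 / 2 = 0.40 kg.

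**Step 3: the same offset in z units.** Approximately gain / reference SD. A flat weight over 6 weeks is a fall of between 0.231 / 12 = 0.019 and 0.808 / 6 = 0.135.

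**Step 4: sampling error.** 95% CI half-width for the mean raw change = t(0.975, n − 1) × SD / √n.

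| n | SD 0.75 kg | SD 1.5 kg |
|---|---|---|
| 6 | 0.787 | 1.574 |
| 9 | 0.577 | 1.153 |
| 12 | 0.477 | 0.953 |
| 15 | 0.415 | 0.831 |
| 30 | 0.280 | 0.560 |

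**Step 5: comparison over 6 weeks.** At 2 kg a year the offset (0.231) is below every half-width. At 7 kg a year with SD 1.5 kg, the offset (0.808) is below every per-dose half-width and above the pooled one (0.560). At 7 kg a year with SD 0.75 kg, it exceeds all of them: just at n = 6 (0.787), and by a factor of nearly two at n = 15 (0.808 / 0.415 = 1.95).

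**The case against.** The strongest reply is that the plan is silent on scale rather than wrong. Section 9.4.4 is a general template; height and weight enter Section 8.2 only as an example of a brief examination, and nothing excludes percentiles or z-scores. That stands, which is why the point concerns the rule as plainly applied. A reader might infer that the plan prescribes a raw kilogram analysis; it does not.

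Second, other data cover much of the ground. Adverse events are reviewed at calls and visits, the UKU scale is completed at Weeks 2, 4 and 6, and Section 9.4.8 lists individual data by measure and time point. Reported appetite loss and each child's recorded weights would still be visible. The listings do not correct a summary mean, but a reader who inferred that marked weight loss would be hidden would be going too far.

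Third, the fix may reach few children. The schedule marks the screening examination with an asterisk tied to the move to virtual visits, and a physician's note may stand in for it. Dosing per kilogram implies that some weight is known, but the number with a study-measured screening weight cannot be determined from the documents. This stands.

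Fourth, the appetite-loss rate comes from epilepsy trials, and Section 4.3 says "Our proposed dosage range is substantially lower than most pediatric studies registered in ClinicalTrials.gov". The rate may not carry over.

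Fifth, a general reference chart may not describe this sample: Part 2 requires ADHD, and stable methylphenidate is allowed. This stands as a limit on the remedy.

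**Conclusion.** The concern holds as a minor one. Applied plainly to weight, the change-from-baseline rule in Section 9.4.4 includes normal growth, and with no control arm the mean can slightly understate slowed weight gain. The direction follows from the arithmetic; the size rests on the assumed growth rates, SDs and interval. It is small in z units, and the 0.5 to 1.9 kg range at 14 weeks applies only to the contingency of a long screening gap.

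It would be tempting to say that sampling error always swamps the offset in a single dose group over 6 weeks. The figures do not support that: with fast growth and the smaller SD, the offset exceeds the half-width even at n = 6. Equally, it should not be read as a material bias. Across most of the assumed range it is within or near the per-dose half-width (0.8 to 1.6 kg at n = 6, 0.4 to 0.8 kg at n = 15) and comparable with the pooled half-width (0.3 to 0.6 kg).

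Nor do the documents support an inference that dosing is affected. The escalation rules and the Part 2 stopping rule in Section 6.1.2 depend on response, not weight, and Section 4.1 calls all endpoints exploratory.

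**What to change.** In Section 9.4.4, for children with a measured screening height and weight, add a descriptive report of change in age- and sex-standardised weight and BMI z-scores, calculated at the exact age on each measurement date. Name the growth reference. Show results pooled and by dose with 95% CIs, beside:
- raw change in kilograms;
- the number with any weight loss;
- the number with a measured screening weight.

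This removes the reference population's average growth over each child's own interval. It does not reduce sampling noise, and without a control arm it does not isolate a drug effect.

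The cost is a few sentences of analysis text and a standard conversion of height, weight, age and sex already collected; no procedure or visit is added. The downsides are dependence on the chosen chart, imprecise per-dose estimates at 6 to 15 children, and no value where a physician's note replaced the screening examination.

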## 1.2 SCHEMA

Pre-trial

Telephone Pre-screening

- Interested parents/legal guardians will speak with study staff over the phone to determine basic inclusionary and exclusionary information
- If the caregiver endorses any exclusionary criteria or fails to endorse inclusionary criteria over the phone, caregivers will be informed that the study would not be appropriate
- If the parent/legal guardian does not endorse any exclusionary criteria and endorses all inclusionary criteria, the study staff will schedule the screening visit
- Of note, if the child does not qualify for the study as a result of pre-screening or the family decides not to proceed with the study after pre-screening, their data will be discarded and will not be used in this research.

Pre-trial

Screening Visit

- Screen n=5 at a time; total n=50 for screening
- Obtain informed consent and assent and patient history
- Screen potential participants by inclusion and exclusion criteria according to the assessments outlined in the Schedule of Activities (SOA)

Day 0

Enrollment/Baseline

- Enroll cohorts of size 3
- Arrive at clinician group consensus on individualized primary target(s) based on results of assessment with parent input
- Administer specified dose of study intervention to the cohort
- Refer to Section 1.3, SOA for battery of baseline assessments

Day 7 +/- 3 days

Follow-up phone call

- Assess for AE

Day 14 +/- 3 days

Assessment of study endpoints and safety

- Administer study intervention
- Refer to Section 1.3, SOA for battery of assessments

Day 21 +/- 3 days

Follow-up phone call

- Assess for AE

Day 28 +/- 3 days

Assessment of study endpoints and safety

- Administer study intervention
- Refer to Section 1.3, SOA for battery of assessments

Day 35 +/- 3 days

Follow-up phone call

- Assess for AE

Day 42 +/- 3 days

End of Study Assessments

- Discontinue study intervention
- Refer to Section 1.3, SOA for battery of assessments
- Group consensus on response to treatment based on the designated target symptom for each study participant

Repeat Screening to Day 42

Repeat with subsequent cohorts

- Following completion of each cohort, a new group of ~5 children will be scheduled for screening
- Enroll subsequent cohort of size 3 and follow the same schedule as above
- Total Enrolled (n = 30; 10 cohorts)

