#### 8.3.4 TIME PERIOD AND FREQUENCY FOR EVENT ASSESSMENT AND FOLLOW-UP

The occurrence of an AE or SAE may come to the attention of study personnel during study visits and interviews of a study participant presenting for medical care.

All AEs including local and systemic reactions not meeting the criteria for SAEs will be captured on the appropriate case report form (CRF). Information to be collected includes event description, time of onset, clinician’s assessment of severity, relationship to study product (assessed only by those with the training and authority to make a diagnosis), and time of resolution/stabilization of the event. All AEs occurring while on study must be documented appropriately regardless of relationship. All AEs will be followed to adequate resolution.

Any medical condition that is present at the time that the participant is screened will be considered as baseline and not reported as an AE. However, if the study participant’s condition deteriorates at any time during the study, it will be recorded as an AE.

Changes in the severity of an AE will be documented to allow an assessment of the duration of the event at each level of severity to be performed. AEs characterized as intermittent require documentation of onset and duration of each episode.

The PI will record all reportable events with start dates occurring any time after informed consent is obtained until 7 (for non-serious AEs) or 30 days (for SAEs) after the last day of study participation. At each study visit, the investigator will inquire about the occurrence of AE/SAEs since the last visit. Events will be followed for outcome information until resolution or stabilization.

---

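### The UKU side-effect scale is first given after dosing starts, so the change from baseline stated for safety endpoints cannot be computed for it

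*Combined protocol and SAP*

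**What the plan says.** Section 8.2, under safety assessment, has the UKU "to be completed by parent/guardian at the Week 2, Week 4, and Week 6 visits". In the Schedule of Activities (Section 1.3) the row "UKU Side Effects Rating Scale" is marked at Study Visits 2, 3 and 4 only. The schema in Section 1.2 places the first dose at the Day 0 enrollment/baseline visit: "Administer specified dose of study intervention to the cohort".

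Section 9.4.4 states the analysis: "Safety endpoints will be analyzed as summary statistics during treatment and as change scores from baselines". It does not list the safety endpoints or name the UKU. It does tie itself to Section 8.2, where the UKU is listed: "The information included here should be consistent with the information contained within" that section.

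For adverse events, Section 8.3.4 says that a condition present at screening "will be considered as baseline and not reported as an AE", although later deterioration is recorded. Section 8.3.5 keeps usual behavioural disruption out of adverse event reporting unless it is far beyond what it was before.

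**The concern.** A change score needs a value from before the drug. The UKU has none, so the analysis in Section 9.4.4 does not fit the schedule for this measure. The symptoms of possible hepatic injury that Section 8.2 attaches to the UKU (fatigue, nausea, vomiting and others) likewise have no scheduled pre-dose query.

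This matters more here than it would in a controlled trial. All participants receive CBD, so there is no concurrent group to show how often a complaint occurs without it. Section 6.1.2 gives further confirmation of the adverse event profile as a purpose of the 9 mg/kg/day extension. What is at stake is whether a complaint recorded at Week 2 can be called new, worse or unchanged.

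**Working it through.** The plan gives no figure that depends on this point, so the check sets the passages side by side.

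**1. Which repeated safety measures have a pre-dose value?** (Sections 1.3 and 8.2)

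| Measure | Before first dose | On treatment | Change computable? |
|---|---|---|---|
| UKU | none | Weeks 2, 4, 6 | no |
| C-SSRS | screening and baseline | Weeks 2, 4, 6 | yes |
| Hepatic and hematologic tests | screening | Week 6; Week 4 if indicated | yes |
| Vital signs | baseline | Week 6 | yes |
| Physical exam with weight | screening, unless a physician's note replaces it | Week 6 | where the exam was done |

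The C-SSRS entry is explicit: "to be completed by the participant at screening, baseline/enrollment, Week 2, Week 4, and Week 6 visits and reviewed by the PI". So is the one for vital signs: "Vital signs will be collected at baseline/enrollment and Week 6 visits". The UKU is the only measure in the table with no pre-dose time point. Text and schedule agree on this, so it is not a table-reading error.

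**2. Do the adverse event rules supply the missing reference?** Only in part. Sections 8.3.4 and 8.3.5 both need a known prior level. That level comes from the history and psychiatric interview at screening, not from an item-by-item rating. Section 8.2 lets more than 8 weeks pass between screening and treatment, with a telephone check of eligibility. The adverse event review row in the Schedule of Activities begins at Telephone Follow-Up 1, after dosing. Under Section 8.3.3.2 a temporal relationship is by itself enough to classify an event as related.

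**3. Do other scales supply it?** For some domains, yes. The SDSC (sleep, including a somnolence subscale), the ABC (irritability), and the SCARED, ASC-ASD and ADAMS (anxiety and mood) are completed before dosing and at Week 6. The documents describe no pre-dose scale for appetite or gastrointestinal symptoms.

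**4. Can the risk be sized?** Section 2.3.1 gives CBD and placebo rates from epilepsy trials. Applied to the Part 2 maximum of 15 children:

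- Somnolence: 36% − 10% = 26 points, × 15 = 3.9 children in excess; placebo 10% × 15 = 1.5.
- Loss of appetite: 28% − 5% = 23 points, × 15 = 3.45; placebo 5% × 15 = 0.75.
- Diarrhea: 31% − 10% = 21 points, × 15 = 3.15; placebo 10% × 15 = 1.5.

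These are adverse event rates in patients with epilepsy, and the section gives no dose for them. They are not pre-dose symptom rates in children with ASD and ADHD, and the documents contain no such rates. The UKU items are not listed either. No estimate follows.

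**5. How many participants could still be given a pre-dose UKU?** The summary of changes mentions a preliminary analysis of 19 participants, and the accrual ceiling is 30. 30 − 19 = 11 at most. Part 1 used 15, so at least 19 − 15 = 4 have already been treated at 9 mg/kg/day without one.

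**The case against.** The strongest reply is that Section 8.2 introduces the UKU as a way of eliciting adverse events, and Section 9.4.4 handles adverse events separately: coded, counted once per participant, and tabulated by severity, frequency and relationship. None of that needs a UKU subtraction. On this view the change-score sentence was meant for laboratory tests, vital signs and the like, and the fault is loose drafting. That is a fair reading, but the sentence covers safety endpoints without exception and the section points to 8.2. At the least the text needs correcting.

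Three stronger readings are tempting and are not supported:

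- A reader might infer that the change-from-baseline safety analysis as a whole cannot be done. The table above shows that the failure is confined to the UKU.
- A reader might infer that the plan treats pre-existing ASD or ADHD symptoms as effects of CBD. Sections 8.3.4 and 8.3.5 instruct the opposite, and Section 8.3.3.2 allows an event to be called not related when another cause is established. Sleep, irritability and anxiety also have pre-dose ratings on other scales, so a pre-dose UKU is not the only possible reference.
- A reader might infer that background complaints would be as frequent as the drug effect sought. On the protocol's own rates the excess is larger than the placebo rate: 26/10 = 2.6 times for somnolence, 23/5 = 4.6 for appetite and 21/10 = 2.1 for diarrhea. Equality would need background rates of 21% to 26%, which no figure in the documents supports.

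It also stands that no termination rule and no part of the primary analysis uses UKU change, and that Section 4.1 calls all endpoints exploratory. These points limit the importance of the gap. They do not remove the mismatch between the schedule and Section 9.4.4.

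**Conclusion.** The point holds in a limited form. No participant is scheduled for a UKU before the first dose, so UKU change from baseline cannot be computed, although Section 9.4.4 as written includes it. This follows from the documents alone and needs no assumption.

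The consequence for interpretation is a risk of misattribution, concentrated in complaints without another pre-dose scale. It rests on three features of the plan: no control arm, reliance on general history for the prior level, and a relatedness rule that timing alone can satisfy. Its size cannot be stated. The matter is worth correcting because the correction is cheap; it does not undermine the primary objective.

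**What to change.** Add the UKU, with the hepatic-symptom query, at Visit 1 before the first dose, in both the Schedule of Activities and Section 8.2, for all remaining participants. Visit 1 is better than screening because the interval between the two can be long.

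In Section 9.4.4, name the safety endpoints and the baseline used for each. Report UKU change from Visit 1, and items that are new or worse than at Visit 1, only for participants with a pre-dose UKU. For those already treated, report on-treatment scores only and state that no change score is available. If nobody remains to be enrolled, the correction to Section 9.4.4 is still needed.

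The cost is a short amendment and one more administration of a form already in use, at a visit the family already attends. Section 8.1 already withholds the first dose until caregiver forms are in. Caregiver burden rises slightly. Earlier participants cannot be repaired, so the 9 mg/kg/day group will be split: at least 4 without a UKU baseline and at most 11 with one, if the 19 in the preliminary analysis are all who had been enrolled. The number with one will be lower if more have since been enrolled or if the rules in Table 3 stop the trial early.
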